### 6.6.2. Sensitivity for the Primary Analyses

The following sensitivity analyses will be performed:

1. A sensitivity analysis will be performed in the ITT Analysis Set in which events occurring from randomization through EoS date (as defined in Section 3.1) will be included. Patients without an event will be censored at the EoS date. Patients lost to follow-up or who otherwise discontinued study prematurely without experiencing any

event will be censored at their EoS date. Patients who did not experience any event before death will be censored at the earlier of the date of death and EoS date.

2. A sensitivity analysis will be performed in the PPS Analysis Set in which events occurring from randomization through end of treatment will be included similar to the On-Treatment Analysis Set.
3. A sensitivity analysis will be performed in the On-Treatment Analysis Set that will additionally censor patients once they start receiving concomitant anticoagulation therapy.
4. A sensitivity analysis will be performed in the On-Treatment Analysis Set that pools the abelacimab dose arms together and compares the pooled abelacimab groups with rivaroxaban.

If the trial is stopping following an independent Data Monitoring Committee (DMC) review, an additional sensitivity analysis will be performed using the data that was used for the DMC analysis where patients without an event will be censored on the earlier of the EoT date or the day of the data cut used for the DMC analysis.

The proportional hazards assumption in the Cox model will be assessed graphically on the Kaplan Meier plot. A piecewise Cox model will be considered if there is evidence of non-proportional hazards.

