#### *Atrial fibrillation studies*

ANT-004 was a randomized, patient-and-Investigator-blinded, placebo-controlled study that evaluated the safety, tolerability, PK, and PD effects of monthly SC administration of abelacimab in AF patients with a CHA2DS2-VASc score of 0-1 in men or 1-2 in women (Yi 2022). A total of 18 patients were randomized, 8 in Cohort 1 (120 mg SC abelacimab or matching placebo) and 10 in Cohort 2 (180 mg SC abelacimab or matching placebo). Repeat SC administration of abelacimab up to 180 mg for 3 months was safe and well tolerated. There were no deaths or SAEs, and no major or CRNM events were reported. In addition, no HSRs or ISRs were reported.

ANT-006 is an ongoing, event-driven, randomized, active-controlled, parallel-group Phase 2b study to evaluate the safety and tolerability of 2 blinded doses of abelacimab compared to open-label rivaroxaban on the rate of major or CRNM bleeding events in patients with AF at moderate-to-high risk of stroke. Patients were randomly assigned 1:1:1 to abelacimab 90 mg SC monthly, abelacimab 150 mg SC monthly, or rivaroxaban oral (PO) daily. Randomization was stratified by concomitant antiplatelet use at baseline and renal function at screening. The 90 and 150 mg abelacimab doses were selected based on a PK/PD model that predicted that these doses would achieve levels of FXI inhibition that bracket the clinically efficacious range. At near steady-state, the 90 mg dose is predicted to provide approximately 80% FXI inhibition at trough while the 150 mg dose is predicted to provide approximately 97% FXI inhibition at trough. The primary safety endpoint is the composite of major and CRNM bleeding events centrally adjudicated by an independent Clinical Events Committee (CEC) blinded to treatment assignment. An independent program-wide Data Monitoring Committee (DMC) is providing oversight of the safety of study participants.

Enrollment was complete in December 2021. A total of 1,287 subjects were randomized with 335 subjects in North America (US and Canada), 896 subjects in EU countries (Czech Republic, Hungary, and Poland), and 56 subjects in Asia (Korea and Taiwan). The mean age of subjects is 73.9 years (range 55-93 years), 44% are female, the mean CHA2DS2-VASc score is 4.7, approximately 20% have a creatinine clearance  $\leq$ 50 mL/min (Cockcroft-Gault equation),

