### 7 Study Completion and Discontinuation

#### 7.1 Study completion and post-study treatment

The SSC will communicate to study sites when the study is ending. Sites will be instructed to schedule an end of treatment period (EoT) visit for randomized patients or end of extension treatment (EoE) visit for extension patients, as relevant:

- Patients assigned to one of the abelacimab treatment arms should have their EoT or EoE visit scheduled approximately 30 days after their last s.c. injection of study medication.
- Patients assigned to the rivaroxaban treatment arm should complete their EoT visit starting approximately two weeks after notification from the SSC. These patients should continue to take their assigned treatment up to the day prior to the EoT visit, at which time rivaroxaban supplies must be collected.

At the EoT visit or EoE (for patients completing the extension period), all study drug supplies must be collected from the patient and the Investigator must begin plans to transition the patient to SoC anticoagulation therapy according to the guidelines in [Table 7-1](#), unless the patient has a contraindication to anticoagulation therapy.

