**Table 7-1 End of Study Transition Guidelines**

Transitioning to	Instructions
Direct oral anticoagulant (DOAC)	Patients should initiate oral DOAC on the same day of the EoT/EoE visit.
Vitamin K antagonist (VKA)	Patients should be given a supply of VKA and instructed to begin therapy 3 to 5 days before the EoT visit. At the EoT visit, measure PT/INR and repeat as frequently as necessary until the PT/INR is therapeutic. Sites may collect repeat INR samples using point of care devices or send for local analysis, in which case results will remain as part of source documentation only.

The EoS visit (in-person or telephone/video-call) will take place approximately 4-weeks after the EoT/EoE visit. This visit will assess patients for a general health and safety check prior to concluding their participation in the study.

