### 3. Analysis Populations and Dates

#### 3.1. Analysis Dates

The analysis dates to be used are defined as:

- EoT date = Earliest of a) the last dose+60 days or b) the EoT visit or c) death date or d) withdraw consent date or e) EoS visit date
- EoS date = Earliest of a) EoS visit or b) death date or c) withdraw consent date or d) lost to follow-up date; if no EoS date available, then impute EoT visit date

In the event that there is an open-label extension period in which the patient enrolls, the following analysis dates to be used are defined as:

- EoT date = Earliest of a) the last dose+60 days or b) the EoT visit or c) death date
- EoS date = Earliest of a) the last dose+60 days or b) the EoT visit or c) death date
- EoE date = Earliest of a) the last dose+60 days or b) the EoE visit or c) death date
- EoS extension date = EoS visit; if no EOS visit date available, then impute EoE date

In accordance with ICH E3 and E9, the following analysis sets will be used for the analyses.

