### 2.1. Change in the EoT date and EoS date in the randomized phase of the study for patients enrolled in the extension in section 3.1 of the SAP

The analysis dates to be used are defined as:

- EoT date = Earliest of a) the last dose+60 days or b) the EoT visit **-1 day** or c) death date or d) withdraw consent date or e) EoS visit date
- EoS date = Earliest of a) EoS visit or b) death date or c) withdraw consent date or d) lost to follow-up date; if no EoS date available, then impute EoT visit date **-1 day**

**As per the protocol version 5.0, EoT visit and Extension Day 1 will occur on same day.** In the event that there is an open-label extension period in which the patient enrolls, the following analysis dates to be used are defined as:

- EoT date = **Earlier of a) the last dose+60 days or b) the EoT visit -1 day**
- EoS date = **the EoT visit -1 day**
- EoE date = Earliest of a) the last dose+60 days or b) the EoE visit or c) death date
- EoS extension date = EoS visit; if no EOS visit date available, then impute EoE date

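### The ITT sensitivity analysis counts about 4 weeks after the end-of-study switch for patients outside the extension but not for extension patients, which probably dilutes its hazard ratio

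*SAP*

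**What the plan says.** **The window.** SAP 6.6.2, item 1, includes "events occurring from randomization through EoS date (as defined in Section 3.1) will be included". Protocol 10.1 and SAP 3.4 set the same end point for the ITT set.

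**Patients outside the extension.** SAP 3.1 gives "EoS date = Earliest of a) EoS visit or b) death date or c) withdraw consent date or d) lost to follow-up date". For a completer this is normally the EoS visit, which "will take place approximately 4-weeks after the EoT/EoE visit" (Protocol 7.1). Protocol 3.1.4 makes 4 weeks the minimum.

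**Extension patients.** SAP 3.1 gives "EoS date = Earliest of a) the last dose+60 days or b) the EoT visit or c) death date". Addendum 2.1, written after database lock, sets the date to "the EoT visit -1 day".

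**The switch.** Abelacimab patients "should have their EoT or EoE visit scheduled approximately 30 days after their last s.c. injection" (Protocol 7.1). In Table 7-1, "Patients should initiate oral DOAC on the same day of the EoT/EoE visit". A vitamin K antagonist starts 3 to 5 days before EoT. Rivaroxaban continues to the day before EoT.

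**FXI inhibition at about the time of the switch.** Protocol 1.2.2 states that near steady state "the 150 mg dose is predicted to provide approximately 97% FXI inhibition at trough", and gives about 80% for 90 mg.

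**Other analyses.** The primary analysis (SAP 6.6.1) stops at the EoT date. Sensitivity analysis 3, which censors when another anticoagulant starts, applies only to the On-Treatment set.

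**The concern.** The weeks between EoT and EoS do not mean the same thing in each arm. A rivaroxaban patient moving to another DOAC exchanges one oral drug for another. An abelacimab patient adds a DOAC about 30 days after the last injection, when predicted trough FXI inhibition is still about 80% or 97%. Any bleed in that overlap is counted against abelacimab, although the second drug was started because the trial ended.

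The window also depends on whether the patient enters the extension. Entry is decided after randomization. It requires site participation, being on treatment at EoT, consent, and freedom from exclusions such as a recent intracranial bleed or low hemoglobin (Protocol 3.1.3, 4.3, 4.4).

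The ITT analysis is the one sensitivity analysis that Protocol 10.4 names for the primary endpoint. If it drifts toward no difference, readers cannot tell a fragile effect from bleeding around the end-of-study switch.

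**Working it through.** **1. The plan's own figure.** Inputs from SAP 2.3: hazard ratio 0.60, 80% power, two-sided alpha 0.05. Events per pairwise comparison (Schoenfeld) = (1.960 + 0.842)² / (0.25 × (ln 0.60)²) = 120.3. With both doses at 0.60, one pair holds (1 + 0.6) / (1 + 0.6 + 0.6) = 72.7% of all events, so the total is 120.3 / 0.727 = 165.4. The stated 166 is reproduced, and 0.60 is a sound starting value.

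**2. Where the window falls.** EoT is at about day 30 after the last injection and EoS about 28 days later, so the extra window is roughly days 30 to 58. It follows the switch for every completer outside the extension. For extension patients it has zero length.

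**3. Inputs for the size.**
- From the documents: rivaroxaban hazard 0.15 per year (15% per year), abelacimab hazard 0.6 × 0.15 = 0.09, dropout hazard −ln(0.90) = 0.105, 400 patients per arm (1,200 / 3), window 28 days = 28 / 365.25 = 0.0767 years.
- Assumed: exponential times; EoT spread evenly over 15 to 27 months, or over 9 to 18 months; share f of completers staying out of the extension; post-switch hazard 0.15 in the rivaroxaban arm and 0.15 × k in an abelacimab arm, with k = 1, 1.5, 2 or 3, constant over the window.

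**4. Formula.** For follow-up F, hazard λ and dropout hazard μ:
- at risk at EoT = exp(−(λ + μ)F)
- events = λ/(λ + μ) × (1 − at risk)
- person-years = (1 − at risk)/(λ + μ)

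Average these over F. Then add f × (at risk) × (1 − exp(−post-switch hazard × 0.0767)) events and f × (at risk) × 0.0767 person-years. The ratio of the two rates approximates the Cox hazard ratio.

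**5. One case in full** (EoT at 15 to 27 months, f = 1, k = 2, per 400 patients):

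| | Rivaroxaban | One abelacimab arm |
|---|---|---|
| Events to EoT | 84.3 | 53.2 |
| Person-years to EoT | 561.9 | 590.8 |
| At risk at EoT | 256.7 | 284.8 |
| Added events | 2.9 | 6.5 |
| Added person-years | 19.7 | 21.8 |

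To EoT: (53.2 / 590.8) / (84.3 / 561.9) = 0.60. To EoS: (59.7 / 612.6) / (87.2 / 581.6) = 0.65.

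**6. All cases.**

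| EoT at | Staying out of extension | k = 1 | k = 1.5 | k = 2 | k = 3 |
|---|---|---|---|---|---|
| 15 to 27 months | all | 0.61 | 0.63 | 0.65 | 0.68 |
| 9 to 18 months | all | 0.62 | 0.65 | 0.68 | 0.74 |
| 15 to 27 months | 20% | 0.60 | 0.61 | 0.61 | 0.62 |
| 9 to 18 months | 20% | 0.60 | 0.61 | 0.62 | 0.63 |

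Cox fits to 400,000 simulated patients per arm agree to within about 0.01.

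**7. Scale.** The planned 166 × 0.727 = 120.7 pairwise events split about 75.5 to 45.3. The standard error of the log hazard ratio is √(1/75.5 + 1/45.3) = 0.19. A move from 0.60 to 0.61 is 0.1 standard errors, to 0.68 about 0.7, and to 0.74 about 1.1.

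**The case against.** **Following everyone to EoS is a conventional ITT choice, and the protocol fixed it.** This stands. It is the reason to keep that analysis rather than replace it after lock.

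**Residual FXI inhibition belongs to the assigned drug.** Protocol 10.1 treats up to 60 days after the last dose as on-treatment (up to EoT), and days 30 to 58 lie inside that span. This stands in part. The carry-over belongs to abelacimab, but the added anticoagulant comes from the trial ending, and the analysis cannot separate the two.

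**Cutting extension patients at EoT is not arbitrary.** On Extension Day 1 they receive open-label abelacimab, including those randomized to rivaroxaban. That justifies their cut-off, but it does not give the other patients the same one.

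**The two harms trade off.** Full dilution needs nobody in the extension, and mixed windows need some patients in it. This stands. The extension may open only after an early stop on DMC advice (Protocol 3.1.3), and the documents do not give its uptake.

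**The multipliers have no source.** This stands. No FXI level or bleeding rate is given for days 30 to 58, and a constant k ignores waning. The 9-to-18-month case is close to a minimum: by September 2022 mean time on treatment already exceeded 12 months and the study was continuing.

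**Rivaroxaban patients can overlap too.** Those moving to a vitamin K antagonist start it while still taking rivaroxaban. This stands, and it is a reason to tabulate by follow-on anticoagulant.

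**Conclusion.** The point holds as a weakness of one sensitivity analysis. Its ITT window takes in the end-of-study switch for completers outside the extension and omits it for extension patients. The likely direction is toward no difference. A true 0.60 would read about 0.61 to 0.68, or 0.62 to 0.74 with shorter follow-up, if nobody enters the extension, and about 0.60 to 0.63 if only 20% stay out. The size rests on the assumed k of 1 to 3 and on the unknown share outside the extension.

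A reader might infer three stronger things that the documents do not support:
- **That the primary result is biased by this window.** For completers it stops at the EoT date. Early discontinuers who move to standard anticoagulation within 60 days of the last dose can carry overlap into it, but that is a separate matter from the end-of-study switch.
- **That the plan favors abelacimab.** The expected shift is against it.
- **That bleeding on the combination is known to be higher.** The overlap is inferred from trough predictions and visit timing, and no rate is reported.

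Nothing here concerns how patients should be switched. It concerns which events each analysis counts.

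**What to change.** 1. Keep the protocol-specified ITT analysis through EoS.
2. Add to SAP 6.6.2 an ITT run that ends for every randomized patient at one common end of the randomized period: the EoT visit minus 1 day, or the equivalent calendar date for patients already off study drug. Tying the cut-off to being on drug at EoT would bring back a post-randomization condition. Protocol 6.6 provides contact about every 12 weeks for early discontinuers until the randomized period ends, so the follow-up is planned. The definition should say that their earlier EoS visit does not end it.
3. Tabulate bleeding from EoT to EoS by arm and by type of follow-on anticoagulant, with the number of patients and person-time at risk. A vitamin K antagonist started 3 to 5 days before EoT leaves a short overlap inside the new run, which a footnote should state.

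Cost: one extra model and one table. The database was locked on 08Mar2024, so both must be labelled as added after lock and shown beside the to-EoS result, so that no events appear to have been removed.

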### **6.6.3. Secondary Analysis**

#### **6.6.3.1. Time to first ISTH-defined major bleeding event**

This endpoint will be analyzed following the procedures outlined in Section [6.6.1](#).

#### **6.6.3.2. Time to first ISTH-defined major or minor bleeding event**

This endpoint is defined as the time to the first ISTH-defined bleeding event equal to or more severe than minor, ie, major bleeding event, CRNM bleeding event, or minor bleeding event. This will be analyzed following the procedures outlined in Section [6.6.1](#).

### **6.6.4. Exploratory Analysis**

[REDACTED]

[REDACTED]

[REDACTED]

[REDACTED]

[REDACTED]

[REDACTED]

[REDACTED]

[REDACTED]

[REDACTED]

[REDACTED]

## 6.7. Safety

### 6.7.1. Extent of Exposure

Duration of exposure to abelacimab will be defined in months as:

- Exposure (months) = ([date of last dose – date of first dose] + 1) / (365.25 / 12)

The duration of exposure to rivaroxaban will be defined in months as:

- Exposure (months) = ([date of last drug returned – date of first drug dispensed] + 1) / (365.25 / 12)

Exposure durations will be calculated regardless of any interruption in dosing between the first and the last dose. If date of first dose date is missing, then date of randomization visit will be used. If last dose date is missing, the patient's EoT date will be used for analysis purpose.

The calculated exposure duration of exposure to abelacimab and to rivaroxaban will be categorized as:

- less than 3 months
- $\geq 3$  months to  $< 6$  months
- $\geq 6$  months to  $< 9$  months
- $\geq 9$  months to  $< 12$  months
- $\geq 12$  months to  $< 15$  months
- $\geq 15$  months to  $< 18$  months
- $\geq 18$  months to  $< 21$  months
- $\geq 21$  months to  $< 24$  months
- $\geq 24$  months

[REDACTED]

[REDACTED]

Duration of exposure will be summarized in two ways for the On-Treatment Analysis Set by treatment group.

- Descriptive statistics will be presented for duration of exposure.
- Number and percentage of patients within each of the exposure categories will be presented.

The proportion of missed doses of abelacimab and the proportion of missed doses of rivaroxaban will be summarized.

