#### **6.4.2 Rivaroxaban**

Each study site will be supplied with cartons of rivaroxaban 20 mg tablets and 15 mg tablets via the IxRS system. On Day 1, patients assigned to rivaroxaban will be given a supply of rivaroxaban and will be instructed to take the first dose that evening with food. Throughout the study, rivaroxaban will be dispensed at appropriate intervals to ensure patients have adequate quantities of study drug between study visits.

In case of circumstances preventing a patient from attending on-site visits, sites may, with the patient's consent, arrange the shipment of rivaroxaban directly to the patient's home as permitted by local regulations. In this case, the Investigator and/or delegated staff will arrange for the courier service and will provide the patient's name and shipping address to the courier.

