## 5. Data Handling

### 5.1. Time Points and Visit Windows

#### 5.1.1. General Definitions

All assessment days will be related to the first day of first dose of treatment.

Day 1 is defined as first dose of treatment. Relative days after Day 1 are calculated as (assessment date – Day 1 date) + 1. Relative days prior to Day 1 are calculated as (assessment date – Day 1 date). The day prior to Day 1 is Day -1. Day 0 is not defined.

The date of the first dose of treatment for each patient will be taken from the electronic case report/record form (eCRF) page. If the date in this eCRF page is missing, alternatively the date of randomization will be used.

The date of the last dose of treatment for each patient will be taken from the eCRF page. For subjects receiving abelacimab, the last dose is latest Date of injection from the Study Drug SC Administration eCRF page.

For subjects receiving rivaroxaban, the last dose will come from the following sources, depending on the patient status:

- For those who permanently discontinue treatment, the last dose will be the permanent discontinuation date.
- For those who died but did not permanently discontinue treatment before death, the last dose will be the death date.
- For all other subjects who completed the treatment per the EoT visit page, the last dose will be the EoT visit date.
- If the last dose date is still missing, the last dose will be the last date pills were returned from the Study Drug PO Accountability page.

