### 2.2. Change in the last dose dates in section 5.1.1 of the SAP

The date of the last dose of treatment for each patient will be taken from the eCRF page. For subjects receiving abelacimab, the last dose is latest Date of injection from the Study Drug SC Administration eCRF page (**before the extension day 1 for patients who enroll in the extension**).

For subjects receiving rivaroxaban, the last dose will come from the following sources, depending on the patient status:

- For those who permanently discontinue treatment, the last dose will be the permanent discontinuation date.
- For those who died but did not permanently discontinue treatment before death, the last dose will be the death date.
- For all other subjects who completed the treatment per the EoT visit page, the last dose will be the EoT visit date **-1 day**.
- If the last dose date is still missing, the last dose will be the last date pills were returned from the Study Drug PO Accountability page.

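### SAP 6.7.1 ends exposure at the last injection for abelacimab but at drug return for rivaroxaban, so patients treated to EoT with equal follow-up show about one month less exposure on abelacimab

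*SAP*

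**What the plan says.** SAP 6.7.1 gives one formula per drug.

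- Abelacimab: "Exposure (months) = ([date of last dose – date of first dose] + 1) / (365.25 / 12".
- Rivaroxaban: "Exposure (months) = ([date of last drug returned – date of first drug dispensed] + 1) / (365.25 / 12".

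The results are shown by treatment group as descriptive statistics and in nine categories, mostly 3 months wide. If the last-dose date is missing, the EoT date is substituted.

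For abelacimab, SAP 5.1.1 settles the end date: "For subjects receiving abelacimab, the last dose is latest Date of injection from the Study Drug SC Administration eCRF page". SAP addendum 2.2 keeps this and only excludes an injection given on extension Day 1.

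For rivaroxaban, addendum 2.2 builds the last-dose date differently from 6.7.1. For completers, "For all other subjects who completed the treatment per the EoT visit page, the last dose will be the EoT visit date", to which the addendum adds minus one day. Pill return enters only if the date is still missing: "the last dose will be the last date pills were returned from the Study Drug PO Accountability page". The addendum leaves the 6.7.1 formulas unchanged.

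Protocol 7.1 fixes how treatment ends. Abelacimab patients "should have their EoT or EoE visit scheduled approximately 30 days after their last s.c. injection of study medication". Rivaroxaban patients "continue to take their assigned treatment up to the day prior to the EoT visit, at which time rivaroxaban supplies must be collected". Both arms start on Day 1: Protocol 3.1.2 makes it the day of first administration, and under Protocol 6.4.2 rivaroxaban patients receive their supply that day and "will be instructed to take the first dose that evening with food".

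On adverse events, Protocol 10.5.1.2 plans exposure-adjusted rates for the On-Treatment Analysis Set. The visible SAP 6.7.3 lists patient numbers, percentages and event counts, and SAP 7 declares no change from the protocol's planned analysis.

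**The concern.** The clock starts on the same day in both arms but stops on different rules. For abelacimab, the month after the final injection is not counted. For rivaroxaban, time runs to the visit at which tablets are handed back. The study is event-driven, so time on drug varies by patient and the exposure table is where a reader checks that the arms were treated for similar lengths of time. Under these rules, two arms with identical follow-up would show different means and different category percentages.

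Two further matters follow. SAP 6.5 computes compliance over the duration of actual treatment exposure without saying whether that is the 6.7.1 duration, and compliance of at least 80% is a condition for the Per Protocol Set. Separately, an analysis that the protocol promises has no visible counterpart in the SAP.

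**Working it through.** The plan states no exposure figure, so there is none to reproduce. The check applies the two formulas to one patient per arm with the same Day 1 and the same EoT visit.

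**Inputs**

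- Days per month: m = 365.25/12 = 30.4375 (SAP 6.7.1).
- Final interval from last injection to EoT visit: f = 30 days (Protocol 7.1). The protocol says approximately and gives no window; 25 to 35 days is my assumption for a range.
- Injection spacing: s = m, one month; N is the number of injections.
- Rivaroxaban returned at the EoT visit (Protocol 7.1).

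**Formulas**

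- Abelacimab: ((N − 1)s + 1)/m
- Rivaroxaban: ((N − 1)s + f + 1)/m
- Difference: f/m = 30/30.4375 = 0.99 month, whatever N is

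| Injections | Abelacimab (months) | Rivaroxaban (months) | Abelacimab lower by |
|---|---|---|---|
| 12 | 11.03 | 12.02 | 8.2% |
| 18 | 17.03 | 18.02 | 5.5% |
| 24 | 23.03 | 24.02 | 4.1% |

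Strict 30-day spacing barely changes this: 10.87 against 11.86 months at 12 injections, or 8.3%. With f from 25 to 35 days, the gap is 25/m = 0.82 to 35/m = 1.15 months: 6.9% to 9.4% at 12 injections, 4.6% to 6.3% at 18, and 3.4% to 4.8% at 24.

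The extreme case is one injection followed by EoT 30 days later: 1/m = 0.03 month, against 31/m = 1.02 months for rivaroxaban.

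**Categories.** A downward shift of 30 days across bands of 3m days moves a share of 30/(3 × 30.4375) = 33% of completers one band lower, if follow-up is spread evenly over 6 to 24 months. That distribution is an assumption; no passage gives one.

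**Rivaroxaban against the SAP's own last-dose date.** For a completer, return is at the EoT visit and the amended last dose is one day earlier: 1/m = 0.03 month. This day is already inside the 30-day difference. Using last dose in both arms would remove only that day and leave 29/m = 0.95 month.

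**Check of the remedy.** End abelacimab at the earlier of last injection + 30 days and the amended EoT date, which for these patients is the EoT visit − 1 day. End rivaroxaban at the EoT visit − 1 day.

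- f = 30: both end at last injection + 29. At 12 injections, ((11 × 30.4375) + 30)/30.4375 = 11.99 months in each arm.
- f = 25: both end at last injection + 24, so they are equal.
- f = 35: abelacimab ends at + 30 and rivaroxaban at + 34, so 4 days remain, or 4/m = 0.13 month.

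**Why not the EoT date alone.** Its rule of last dose + 60 days would credit 61/m = 2.00 months to a patient who stopped after one injection or one day of rivaroxaban.

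**The case against.** Last dose minus first dose plus one is an ordinary definition of dosing duration. The SAP states each rule openly, the documents name no single true exposure, and missed doses and compliance are reported separately. All of that is fair and limits the weight of the point. It does not make the arms comparable. The rivaroxaban formula does not follow that convention, and a last-dose rule in both arms would still set a monthly injection against a daily tablet. The documents themselves treat an injection as acting beyond its date: Protocol 1.2.2 predicts about 80% and 97% FXI inhibition at trough for the two doses, and SAP 3.1 allows on-treatment status to last up to 60 days after the last dose.

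It also stands that the 30-day credit is one option. It comes from a visit-scheduling rule, and the documents use other intervals elsewhere: more than 45 days for recording an abelacimab interruption (Protocol 6.5) and 60 days for on-treatment status.

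Three stronger readings are tempting but unsupported.

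- A reader might infer that abelacimab AE rates would be inflated. No visible passage makes the 6.7.1 duration the denominator of any rate, and SAP 6.7.3 counts events up to the end-of-study visit, a different window.
- A reader might infer that the SAP has dropped the exposure-adjusted rates altogether. Two lines of 6.7.1 and all of 6.6.4 are redacted, and the TFL shells are not available here, so absence is shown for the visible text only. Extension-period rates may belong to the separate extension SAP.
- A reader might infer that no inferential result could depend on the definition. The possible link through 6.5 to the Per Protocol sensitivity analysis leaves that open.

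**Conclusion.** The point holds for patients treated to an EoT visit scheduled under Protocol 7.1. For equal follow-up, reported abelacimab exposure is about 0.99 month shorter: about 8% at 12 months, 5.5% at 18 and 4% at 24. Protocol 1.2.2 reports mean time on treatment already above 12 months in September 2022 with the study ongoing, so the lower percentages are probably closer to the final table. After early discontinuation or death, the gap depends on the time since the last injection and on when tablets come back; no single figure applies.

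The shown effect is confined to the descriptive means and categories. The primary and secondary bleeding analyses run to the EoT date (SAP 6.6.1 and 6.6.3, addendum 2.1) and do not use the 6.7.1 duration. Whether Per Protocol membership depends on it cannot be settled from the text. This is worth correcting, but does not threaten the main results.

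The missing exposure-adjusted AE rates are a separate discrepancy between protocol and visible SAP, held with moderate confidence.

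**What to change.** 1. In SAP 6.7.1, end abelacimab exposure at the earlier of last injection plus one dosing interval (30 days) and the EoT date of Section 3.1 as amended. End rivaroxaban exposure at the last-dose date of Section 5.1.1 as amended. Patients treated to EoT then agree across arms to within a few days, and exactly when the final interval is 30 days.
2. In SAP 6.5, state whether actual treatment exposure means this duration.
3. In SAP 6.7.3, restore the exposure-adjusted AE rates for the On-Treatment Analysis Set, with person-time over the same window as the events counted, or declare their removal in SAP 7.

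The first item needs new wording for two definitions, one derived variable reprogrammed and the exposure tables rerun, with no new data. If 6.5 does use this duration, compliance, Per Protocol membership and that sensitivity analysis need rechecking. Restoring the rates adds a person-time derivation and tables. The addendum already records changes made after database lock, so these can be documented in the same way.
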